820 or <70 mg/dL or ketones ≥ 1.5 mmol/L.

821 **5.2.2 Home Use of the Study System**

822 After training on the study system has been completed, participants will proceed with home use
823 (meaning free-living use at school, home, etc.) of the t:slim X2 with Control-IQ technology
824 system.

825 Participants may use available manufacturer-provided software and features of the study CGM
826 related to mobile data access or remote monitoring, but will be instructed not to use any third-party
827 components for this purpose.

828 **5.2.3 Study Device Download**

829 Participants will be instructed to download the study device prior to each phone visit or on at least
830 every 3-week basis throughout the remainder of the study.

831 **5.2.4 1-Week Phone Contact**

832 Study staff will perform a phone call with the participant within 7 (± 1) days following
833 randomization.

834 The following will occur:

- 835 • Assessment of compliance with study device use by review of any available device data
- 836 • Assessment of adverse events, adverse device effects, and device issues
- 837 • Study staff will answer any questions related to device use

838 Participants will then complete an additional week of home use with the study system. Participants
839 will return to clinic 14 (± 3) days from the date of randomization.

840 **5.2.5 2-Week Visit (Training Review and Insulin Pump Optimization)**

841 The participant will be offered review training to address any questions on the use of the study
842 device including meal bolus strategies and strategies related to pump use and exercise.

843 The following will occur:

- 844 • Assessment of compliance with study device use by review of any available device data
- 845 • Assessment of adverse events, adverse device effects, and device issues
- 846 • Study staff will answer any questions related to device use and follow the procedure for insulin
847 pump optimization described in section 3.6 using the study CGM available data from the
848 previous two weeks.
- 849 • The blood glucose meter and study ketone meter will be downloaded and QC tested with
850 control solution.

851 **5.3 Procedures for the SC Group**

852 Participants in the SC group will use an insulin pump that they usually use for the treatment of
853 their diabetes or a study pump provided by the study team if they are transitioning from MDI to
854 pump for the study, in conjunction with the study CGM, study blood glucose meter, and study

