1189 labeled or marketed. (21 CFR 803.3). Note: for reporting purposes, clinical centers will not be
1190 asked to distinguish between device complaints and malfunctions.

1191 **9.1.2 Reportable Adverse Events**

1192 For this protocol, a reportable adverse event includes any untoward medical occurrence that meets
1193 one of the following criteria:

- 1194 1. A serious adverse event
- 1195 2. An Adverse Device Effect as defined in section 9.1.1, unless excluded from reporting in section
1196 9.2
- 1197 3. An Adverse Event occurring in association with a study procedure
- 1198 4. Hypoglycemia meeting the definition of severe hypoglycemia as defined below
- 1199 5. Diabetic ketoacidosis (DKA) as defined below or in the absence of DKA, a hyperglycemic or
1200 ketosis event meeting the criteria defined below

1201 Hypoglycemia and hyperglycemia not meeting the criteria below will not be recorded as adverse
1202 events unless associated with an Adverse Device Effect. Skin reactions from sensor placement are
1203 only reportable if severe and/or required treatment.

1204 Pregnancy occurring during the study will be recorded.

1205 **9.1.2.1 Hypoglycemic Events**

1206 Hypoglycemia not associated with an Adverse Device Effect is only reportable as an adverse event
1207 when the following definition for severe hypoglycemia is met: the event required assistance of
1208 another person due to altered consciousness, and required another person to actively administer
1209 carbohydrate, glucagon, or other resuscitative actions. This means that the participant was
1210 impaired cognitively to the point that he/she was unable to treat himself/herself, was unable to
1211 verbalize his/ her needs, was incoherent, disoriented, and/or combative, or experienced seizure or
1212 coma. These episodes may be associated with sufficient neuroglycopenia to induce seizure or
1213 coma. If plasma glucose measurements are not available during such an event, neurological
1214 recovery attributable to the restoration of plasma glucose to normal is considered sufficient
1215 evidence that the event was induced by a low plasma glucose concentration.

1216 **9.1.2.2 Hyperglycemic Events/Diabetic Ketoacidosis**

1217 Hyperglycemia not associated with an Adverse Device Effect is only reportable as an adverse
1218 event when one of the following 4 criteria is met:

- 1219 • the event involved DKA, as defined by the Diabetes Control and Complications Trial (DCCT)
1220 and described below

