311 *Boxplots*

312 Boxplots stratified by treatment group will be given for the primary outcome and each of the key
313 secondary endpoints listed in Section 6.2.1 in 4week and 1-week periods over the course of 16 weeks
314 intervention.

315 **7. Safety Analyses**

316 All randomized participants will be included in these analyses and all their post-randomization safety
317 events will be tabulated. Events occurring from the randomization date until and including the 16-week
318 visit date or randomization date + 126 days whichever is earlier will be included.

319 Any pre-randomization adverse events will be tabulated separately and will include participants who
320 were never randomized.

321 For the following outcomes, mean \pm SD or summary statistics appropriate to the distribution will be
322 tabulated by treatment group and formal statistical comparisons will be performed if there are enough
323 events (at least 5 events combined over both treatment groups):

- 324 • Number of SH events and SH event rate per 100 person-years
- 325 • Number of DKA events and DKA event rate per 100 person-years
- 326 • Any adverse event rate per 100 person-years
- 327 • Number of calendar days with any ketone level ≥ 1.0 mmol/L (if ≥ 5 total calendar days
328 combined)
- 329 • CGM-measured hypoglycemic events (≥ 15 minutes with glucose concentration < 54 mg/dL)
- 330 • CGM-measured hyperglycemic events (≥ 15 minutes with glucose concentration > 300 mg/dL)

332 If there are at least 5 SH events combined over both treatment groups, the rates will be compared using a
333 robust Poisson regression. The regression will adjust for the participant-reported number of SH events
334 12 months prior to the start of the study and clinical center as random effect. The amount of follow up
335 will be included as an offset covariate to compare the rates. If one of the treatment groups has zero
336 events then a Poisson model will not converge and Fisher's exact test will be used instead. A similar
337 analysis will be done for DKA if there are at least 5 total DKA events among both treatment groups
338 combined. For any adverse event and number of calendar days with ketone event, similar analyses will
339 be done except that clinical center will be the only covariate to be adjusted in the model.

340 The calculation for the two continuous CGM-measured outcomes will be based on the same inclusion

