341 criteria mentioned above for the primary outcome. The event rates per week will be compared using
342 similar linear mixed effects regression models as described above for the primary outcome.

343 The following will be summarized and tabulated by treatment group:

- 344 • Other serious adverse events (SAE)
- 345 • BG-measured hypoglycemic events (days with at least one BG record < 54 mg/dL)
- 346 • BG-measured hyperglycemic events (days with at least one BG record > 350 mg/dL)
- 347 • Worsening of HbA1c from baseline to 16 weeks by $> 0.5\%$
- 348 • Related to Investigational Device Usage (intervention group only):
 - 349 ○ Adverse device effects (ADE)
 - 350 ○ Serious adverse device events (SADE)

351 ○ Unanticipated adverse device effects (UADE)

352 **8. Intervention Adherence**

353 *Closed Loop System*

354 The amount of closed loop system use for the CLC group will be calculated from downloaded data over
355 the period from the day after randomization until the day before the 16 week visit. Any dropouts will be
356 counted as zero use for the remainder of the study.

357 Percent time in different operation modes overall and by 4-week periods will be tabulated and boxplots
358 will be created by 4-week periods.

359 *CGM Use*

360 The amount of CGM sensor use for both treatment groups will be calculated from downloaded data in
361 the same way as closed-loop system use described above.

362 Percent time sensor use overall and by 4-week periods will be tabulated by treatment group and boxplots
363 will be created by 4-week periods.

364 *Blood Glucose Monitoring*

365 Average daily frequency of downloaded BGM use for both treatment groups will be calculated similarly
366 in the same time window. If a participant drops out of the study or no meter download is available for a
367 specific period, average daily BGM use will be set to missing for that period.

368 The average daily frequency of downloaded BGM use overall and by 4-week periods will be tabulated
369 by treatment group.

370 **9. Protocol Adherence and Retention**

371 The following tabulations and analyses will be performed by treatment group to assess protocol
372 adherence for the study:

373 • Number of protocol and procedural deviations
374 • Flow chart accounting for all enrolled participants up to randomization
375 • Flow chart of all randomized participants at all scheduled visits and phone contacts post
376 treatment initiation

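### The any-AE rate comparison pools in device-attributed events that the SC arm may capture less fully; a restricted comparison should be pre-specified beside it

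*SAP*

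**What the plan says.** **The comparison.** SAP section 7 lists "Any adverse event rate per 100 person-years" among the outcomes to be formally compared if there are enough "events (at least 5 events combined over both treatment groups"). The method is the robust Poisson model used for severe hypoglycemia, with follow-up as an offset. For this outcome the analysis will "be done except that clinical center will be the only covariate to be adjusted in the model". Protocol 11.8 plans the same. Neither document splits the total by device relatedness.

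**What counts as an event.** Only reportable events enter the database (Protocol 9.1.2). Besides serious events, severe hypoglycemia, and DKA or other qualifying hyperglycemia/ketosis, the criteria include "An Adverse Event occurring in association with a study procedure" and "An Adverse Device Effect as defined in section 9.1.1, unless excluded from reporting in section" 9.2. Glucose excursions short of the definitions are not to be recorded as adverse "events unless associated with an Adverse Device Effect. Skin reactions from sensor placement are" reportable only when severe or treated.

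**Which device.** Protocol 9.1.1 defines an adverse device effect (ADE) for any participant and refers simply to the device. Protocol 9.1.3 has the investigator judge relatedness to the study device.

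**Who wears what.** In CLC the personal pump is removed and the study pump started (Protocol 5.2). For the other arm, Protocol 5.3 says "Participants in the SC group will use an insulin pump that they usually use for the treatment of" their diabetes, or a study pump if they come from injections. Both arms wear the study CGM.

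**Display.** SAP section 7 tabulates ADEs, SADEs and UADEs under the line "Related to Investigational Device Usage (intervention group only"; Protocol 11.8 does likewise.

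**The concern.** A between-arm test of event rates is interpretable only if the same occurrence would be recorded in either arm. For one class of event, recording depends on whether the investigator links it to the study device. A milder glucose event after a pump fault can pass that test when the pump is the study pump. It may not when the pump is the child's own, because neither document says whether a personal pump counts as the device.

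If such events go unrecorded in SC, the rate ratio reflects ascertainment as well as safety, and the error runs against CLC. The p-value is not adjusted for multiplicity (SAP section 14), and the data may support a marketing application (Protocol 1.2 and 11.13).

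**Working it through.** **1. Which events depend on device attribution?**

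| Class | Depends on attribution? | Capture by arm |
|---|---|---|
| Serious events | No | Alike |
| Severe hypoglycemia (9.1.2.1) | No | Alike |
| DKA, or hyperglycemia/ketosis meeting 9.1.2.2 | No | Alike |
| Study-procedure events | No | Alike |
| ADE-only events, CGM-related | Yes | Study CGM in both arms |
| ADE-only events, pump-related | Yes | Study pump for all CLC; in SC only for children from injections |

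Only the last row is exposed, and it is narrowed twice. Section 9.2 lists anticipated issues kept off the Device Issue Form, including disconnections and occlusions without ketosis. Section 9.1.2.2 makes an event reportable in either arm if ketones reach 1.5 mmol/L with provider contact or 3.0 without it, or if facility care was obtained. What remains is milder pump-related events outside both provisions.

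**2. Exposure.** The plan gives no event rate or power for this comparison, so it has no figure of its own to reproduce. Its one design figure, N = 60 for the primary outcome, does reproduce: (1 + 1/3) × (1.960 + 1.282)² × (10/10)² = 14.01, rounded up to 15 SC plus 45 CLC. It is not affected by this point. At N = 100 allocated 3:1, with full follow-up assumed:

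- CLC: 75 × 16/52 = 23.1 person-years
- SC: 25 × 16/52 = 7.7 person-years

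**3. Apparent rate ratio when true rates are equal.** Let *s* be the share of all events that are ADE-only, and *f* the fraction of those captured in SC relative to CLC. Both are assumptions.

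Apparent ratio (CLC:SC) = 1 / (1 − *s* + *f s*)

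| *s* | *f* = 0 | *f* = 0.5 | *f* = 1 |
|---|---|---|---|
| 10% | 1/0.90 = 1.11 | 1/0.95 = 1.05 | 1.00 |
| 25% | 1/0.75 = 1.33 | 1/0.875 = 1.14 | 1.00 |
| 50% | 1/0.50 = 2.00 | 1/0.75 = 1.33 | 1.00 |

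The column *f* = 0 is an extreme. Suppose no personal-pump event is captured, a share *m* of SC children wear a study pump, and a share *c* of ADE-only events are CGM-related. Then *f* = *c* + (1 − *c*)*m*. Taking *m* = 0.20 (the Protocol 2.1 recruitment minimum for injection users, assumed to hold within SC) and *c* = 0 gives *f* = 0.20. At *s* = 50% the ratio is then 1/(0.50 + 0.10) = 1.67, not 2.00.

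The small SC exposure makes the ratio fragile. At an assumed 100 events per 100 person-years, SC expects 7.7 events. Missing two gives 7.7/5.7 = 1.35.

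**4. Chance of a false 'CLC worse' result.** This uses an exact conditional binomial test as a stand-in for the robust Poisson model, at two-sided 0.05, with the five-event trigger and equal true rates.

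| Assumed rate per 100 person-years | *s* | *f* = 0 | *f* = 0.5 | *f* = 1 |
|---|---|---|---|---|
| 50 | 25% | 3.2% | 2.0% | 1.3% |
| 50 | 50% | 7.9% | 3.2% | 1.3% |
| 100 | 25% | 5.8% | 3.0% | 1.5% |
| 100 | 50% | 19.1% | 5.8% | 1.5% |
| 200 | 25% | 11.2% | 4.8% | 1.9% |
| 200 | 50% | 43.1% | 11.2% | 1.9% |

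At modest rates and partial capture the test is little disturbed, and the damage is mainly to the estimated ratio. The test is seriously misleading only when events are frequent, device effects are a large share, and SC capture is poor.

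**The case against.** A reader might infer from the intervention-group-only line that the arms have different reporting rules and that device effects are reportable essentially only in CLC. The documents do not support this. The criteria in 9.1.2 carry no arm restriction. The ADE definition covers any participant. Device effects are asked about at the SC contacts (Protocol 5.3.2, 5.3.3) and at later contacts in both groups (5.4). SC children wear the study CGM, and Protocol 10.2 counts the study CGM among the investigational devices. The quoted line governs a table, not collection, and SAP section 11 reports device issues for both arms.

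Three further objections carry weight.

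- Sections 9.2 and 9.1.2.2 remove many pump problems from dispute. This stands, and it confines the point to milder events.
- Harm truly caused by the CLC device belongs in the treatment effect, and dropping it from the only formal test would be a poor default for a device trial. This stands, and it is why the all-event comparison should remain.
- The plan already compares severe hypoglycemia, DKA, ketone days and CGM-measured events separately. These help a reader, and the measured outcomes need no attribution. But none shows whether a difference in the any-AE total comes from ADE-only events, and the planned ADE table has no SC column.

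It can also be said that the error runs against the sponsor's device and is therefore conservative. That limits the harm, but it does not make the ratio a fair estimate.

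**Conclusion.** A limited weakness stands. The any-AE total includes a class of events whose capture in SC personal-pump users is undefined, and under-capture there would raise the CLC:SC ratio. With equal true rates and ADE-only events at 10–50% of the total, the apparent ratio is about 1.05–1.33 if SC captures half and 1.11–2.00 if it captures none. The share, the capture fraction and the underlying rate are all assumptions. The documents give none of them, so these are ranges and not an estimate of the bias.

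An observed excess on CLC would not by itself show biased ascertainment, since it could be real device harm. As planned, the comparison cannot tell the two apart. The primary outcome and the hierarchical tests are unaffected.

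**What to change.** In SAP section 7 and Protocol 11.8:

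- Keep the all-event comparison as planned.
- Pre-specify beside it the same model on events that meet at least one criterion other than ADE, that is, excluding events reportable solely as ADEs.
- Tabulate the excluded events by arm and by device (study pump, personal pump, CGM), without a p-value.
- State that any difference in the any-AE rate will be interpreted in light of both comparisons.

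Under the assumptions above, the restricted ratio is 1.00 whatever SC captures, because it leaves out the class where loss can occur. It does not recover SC events that were never recorded.

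The cost is one derived flag and one table, assuming the adverse-event and device-issue forms identify the criterion met and the device involved. The restricted comparison also has fewer events: at 100 per 100 person-years and *s* = 50%, SC would expect 7.7 × 0.5, or about 3.8.

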Appendix: Example for Hierarchical Testing

508

509 In the hypothetical scenario depicted in the table below, the first four outcome variables all have a
 510 significant result so testing continues to the fifth variable (CGM % below 70 mg/dL). The result is not
 511 significant for that fifth variable ($p = 0.06$) so testing stops. No formal hypothesis test is conducted for
 512 the last three variables on the list in this example scenario.

513

514 **Table. Example Hierarchical Test Results**

HIERARCHICAL ORDER	OUTCOME VARIABLE	TREATMENT ARM P-VALUE	SIGNIFICANT?	ACTION
1 st	CGM % 70-180 mg/dL (primary outcome)	0.001	Yes	Test next variable
2 nd	CGM % above 180 mg/dL	0.02	Yes	Test next variable
3 rd	CGM mean glucose	0.007	Yes	Test next variable
4 th	HbA1c at 16 weeks	0.03	Yes	Test next variable
5 th	CGM % below 70 mg/dL	0.06	No	Stop formal testing
6 th	CGM % below 54 mg/dL	Not tested	Unknown	N/A
7 th	CGM % above 250 mg/dL	Not tested	Unknown	N/A
8 th	Glucose CV	Not tested	Unknown	N/A

515
